#### Reporting of SAEs to Regulatory Authorities

The CRCTU, Birmingham will report all fatal or life threatening SUSARs to the Medicines and Healthcare products Regulatory Agency (MHRA) and the Multi-Centre Ethics Committee (MREC) within 7 days of receiving initial notification from the study site. Any follow-up information will be provided within an additional 8 days. Non-fatal and non-life threatening SUSARs will be reported within 15 days. The CRCTU, Birmingham will submit an Annual Safety Report to the MHRA and MREC summarising all reported SARs.

The CRCTU, Birmingham will forward details of SUSARs to all Investigators in the form of an Annual Safety Report. SAEs will be reported to the relevant Pharmaceutical Companies as appropriate.

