## 8. TREATMENT DETAILS

### 8.1 Trial plan

**Treatment should begin within 5 working days of randomisation. The planned duration of treatment is 16 weeks.**

## **Subjects will be randomised (1:1:1:1) to receive either:**

### **Exemestane + Celecoxib**

Patients will receive exemestane 25mg, one tablet daily and celecoxib 400mg, one capsule twice daily

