### **Letrozole + Celecoxib-Placebo**

Patients will receive letrozole 2.5mg, one tablet daily and celecoxib-placebo, one capsule twice daily

Treatment in all arms will continue until the day of surgery (patients should not take study medication after requirement of 'nil by mouth' for anaesthetic purposes). The surgical date should be planned in advance and will be between 16 weeks and 18 weeks from the commencement of treatment. Sufficient drug supplies will be included to cover this 2-week window.

Dose modifications of trial treatment are not permitted. Patients who are unable to tolerate the trial treatment should be withdrawn from study.

Patients whose tumours progress during the neoadjuvant phase will be withdrawn from study and treated according to local practice.

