## **15.2 Informed Consent**

It is the responsibility of the local Investigator to obtain fully Informed Written Consent from each patient prior to inclusion in the trial or, where relevant, prior to evaluating the patient's suitability for the trial. The approved Patient Information Sheet should be given to each patient prior to randomisation, with the risks and benefits of participating in the trial clearly explained. The patient should be given ample time to read the information sheet and the opportunity to inquire about details of the trial. They should also be given time to discuss their participation with others outside of the clinical trials team and given another opportunity to ask the clinician and the research nurse questions regarding their participation in the study if required. All questions or concerns about the trial should be answered to the satisfaction of the patient. Sufficient time should be allowed (at least 24 hours) for the patient to reach a decision. It should be explained that they are free to refuse to take part and informed about their right to withdraw from the trial at any time. If the patient agrees to take part in the trial they should be asked to sign and date the approved Informed Consent Form, which should also be signed and dated by the Investigator. A copy of the Informed Consent Form should be given to the patient, a copy filed in the hospital notes and a copy filed in the Investigator Site File. Throughout the study the patient should have the opportunity to ask questions about the trial and any new information that may be relevant to the patient's willingness to continue participation in the trial should be shared with the patient in a timely manner.

The Informed Consent Form and Patient Information Sheet will be available in electronic format from the NEO-EXCEL Study Office to enable individual hospitals to copy onto their headed paper. A copy of the Informed Consent Form and Patient Information Sheet is included in Appendices 7 and 8 for information. The Breast Biopsy Patient Information Sheet and Consent is included in Appendices 9 and 10.

With the patient's consent their General Practitioner (GP) should be informed about their participation in the trial. The approved GP Information Letter (Appendix 11) should be sent to the GP, along with any other related correspondence.

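### The only stated route for telling investigators of SUSARs is an annual report, so most patients on drug at other sites would finish their 16-18 week course before it arrives

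*Protocol*

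**What the plan says.** **Regulator and ethics committee.** Under the heading on reporting SAEs to regulatory authorities in Protocol section 13.3, fatal or life-threatening SUSARs go to the MHRA and the MREC "within 7 days of receiving initial notification from the study site". For the rest, "Non-fatal and non-life threatening SUSARs will be reported within 15 days".

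**Investigators.** The same subsection says that the coordinating unit "will forward details of SUSARs to all Investigators in the form of an Annual Safety Report". No shorter interval is given for them.

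**Length of treatment.** Section 8.1 says "The planned duration of treatment is 16 weeks". It adds that "Treatment in all arms will continue until the day of surgery", and that the surgical date "will be between 16 weeks and 18 weeks from the commencement of treatment".

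**Duty to patients.** Section 15.2 says that new information bearing on a patient's "willingness to continue participation in the trial should be shared with the patient in a timely manner".

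**The concern.** A SUSAR is, by the definitions in section 13.1, a serious reaction that the product information did not lead anyone to expect. It is therefore the kind of event that could change a patient's mind about continuing. The duty in section 15.2 is carried out by the site investigator, who can pass on only what has reached the site.

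The protocol sets the frequency at which sites hear of SUSARs, and sets it at a year, when a patient's whole course takes about four months. The trials unit, the regulator and the ethics committee would know within days or weeks. Investigators at the other sites could go on treating and consenting patients without that knowledge.

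This is a rule the protocol itself fixes, not a detail left to another document. It does not touch the primary endpoint or the analysis. What is at stake is whether patients and their investigators have the information in time to use it.

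**Working it through.** The protocol gives no figure on this point, so there is none to reproduce. The check is one of timing.

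**Inputs from the protocol**
- Treatment length *T*: 16 weeks planned, up to 18 weeks because drug continues to surgery (section 8.1).
- Interval between notices to investigators: annual (section 13.3), taken as 52 weeks.
- Expedited clocks: 7 and 15 days (section 13.3).

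**Assumptions not in the protocol**
- A SUSAR is equally likely at any time in the cycle, so the wait *W* to the next report is uniform on 0 to 52 weeks, with mean 26 weeks.
- Recruitment is steady, so a patient on drug at that moment has remaining treatment *R* uniform on 0 to *T*.
- The report reaches sites on the day the cycle ends. This is relaxed below.

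**Share of on-drug patients who finish before the report**

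P(*R* < *W*) = 1 − (*T*/2)/52

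| *T* (weeks) | Calculation | Finish before report |
|---|---|---|
| 16 | 1 − 8/52 | 84.6% |
| 17 | 1 − 8.5/52 | 83.7% |
| 18 | 1 − 9/52 | 82.7% |

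A simulation of 2,000,000 draws for each *T* agrees (84.6%, 83.7%, 82.7%). The complement, 15.4% to 17.3%, is the share still on drug when the report comes.

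**How it varies over the year**
- Every patient on drug at the time has finished if *W* > *T*. The chance is (52 − 16)/52 = 69.2% for 16 weeks and (52 − 18)/52 = 65.4% for 18 weeks.
- Fewer than half have finished only if *W* < *T*/2, that is, if the SUSAR falls in the last 8 to 9 weeks of the cycle. The chance is 8/52 = 15.4% to 9/52 = 17.3%.

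**Allowing for time to prepare the report.** With a lag of *L* weeks after the cycle ends, the share is 1 − (*T* − *L*)²/(2 × 52 × *T*).
- *L* = 4: 1 − 144/1664 (*T* = 16) and 1 − 196/1872 (*T* = 18), about 91% and 90%.
- *L* = 8: 1 − 64/1664 and 1 − 100/1872, about 96% and 95%.

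**If sites were told on the expedited clocks.** Counting the clock from the SUSAR, the share who finish first is (days/7)/*T*.
- 7 days: 1/18 to 1/16, or 5.6% to 6.25%.
- 15 days: 2.14/18 to 2.14/16, or 11.9% to 13.4%.

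**Search for another route**
- Section 10.4 keeps the Trial Coordinator in regular contact with sites, but about progress and queries.
- Section 10.7 gives the Trial Steering Committee oversight of patient safety, with no duty to notify sites.
- Section 10.8 has the IDMC first review data on 400 patients, then meet annually and advise the steering committee in confidence.
- Section 13.4 only acknowledges SAE forms by fax.
- Section 13.5 covers unblinding.
- Section 15.1 preserves a clinician's responsibility to act at once, but gives no means of being informed.

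None of these tells other sites about a SUSAR sooner.

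**The case against.** **There is no strict contradiction.** Section 13.3 does not say that the annual report is the sole notice, and it does not bar an earlier one. Section 15.2 covers information that may matter to a patient's decision, which need not be every SUSAR. A yearly summary and ad hoc alerts could coexist. This stands: the two sections fit badly together, but neither excludes the other.

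**Others are watching in the meantime.** Clinical Coordinators independently assess each SAE, and the MHRA and MREC hear quickly. A reader might infer that nobody would act on a hazard for a year, and the protocol does not support that. Still, none of these safeguards promises that sites will be told.

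**Detail may sit elsewhere.** Section 13 says reporting follows the EU Directive and UK legislation, and section 13.5 points to the Investigator Site File for an out-of-hours procedure. A faster site procedure may exist there. It cannot be assumed, but it limits confidence in the practical consequence.

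**The percentages measure timing, not harm.** They rest on even timing and steady recruitment, and the protocol gives no expected number of SUSARs. This stands too. In essence they show that a four-month course is short against a yearly report.

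**Celecoxib's cardiovascular risk.** A reader might infer that the excess reported in the APC trial makes the delay especially dangerous. Section 3.5.2 already sets that finding before every investigator, and section 6.2 excludes patients with several cardiovascular conditions. A SUSAR concerns reactions outside the product information, so a known risk is weak support for faster notice of unknown ones.

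**Conclusion.** The point holds as a badly fixed rule, with moderate confidence. As written, the only stated route for SUSAR information to investigators is annual, while the regulator and ethics committee are served in 7 or 15 days.

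Assuming a 52-week cycle, even SUSAR timing, steady recruitment and no preparation lag, about 83-85% of patients then on drug at non-reporting sites would finish first. A preparation lag raises that share. The average does not apply to a SUSAR just before the report date, and the site that reported the event already knows of it.

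A reader might go further and say that the annual rule is useless to anyone still on treatment. The same calculation rules that out: some 15-17% of on-drug patients would still be on treatment when the report came.

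**What to change.** Reconcile sections 13.3 and 15.2 with one added sentence in 13.3, for example: *A version of each SUSAR report that does not reveal the celecoxib/placebo allocation will be sent to all Principal Investigators when the 7- or 15-day expedited report is submitted; the Annual Safety Report remains as a cumulative summary.* If the site file already contains a faster route, 13.3 should state it.

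The cost is one e-mail or fax per SUSAR, since the report is already written for the regulator. The downside is a little extra mail and a small risk of hinting at allocation, because section 13.5 has the coordinating centre unblind events thought to be related. That is why the site version must be specified as masked. Nothing in treatment, endpoints or analysis changes.

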### 13.4 Follow-up of AEs/SAEs

All AEs will be recorded on the CRFs until 30 days after the last treatment dose on study or until the start of other anti-cancer treatment, whichever occurs first. Additionally, all AEs deemed possibly related to the trial medication will be followed until resolution, or the Investigator assesses them to be chronic or stable, or initiation of other anti-cancer therapy, whichever occurs first.

In the case of SAEs, the subject must be followed-up until clinical recovery is complete and laboratory results have returned to normal, or until disease has stabilised. Follow-up may continue after completion of protocol treatment if necessary. Follow-up information will be collected on a new SAE form. Follow-up information need not be signed off by an Investigator. Extra annotated information and/or copies of test results should also be provided where available.

Receipt of all SAE forms will be acknowledged via fax.

### 13.5 Codebreaks

Codebreaks should be avoided whenever possible. Approval must be given from one of the NEO-EXCEL Clinical Coordinators before a codebreak is undertaken. This will be checked before the code is broken (except in emergency situations). Unblinding should only be undertaken for medical reasons. When assessing SAEs both Investigator and Clinical Coordinator must assume that the patient received the IMP (i.e celecoxib and not the celecoxib-placebo). If the event is thought to be related, unblinding will be performed by the coordinating centre.

**Refer to Investigator Site File/Pharmacy File for procedure outwith office hours.**

## 14. STATISTICAL CONSIDERATIONS

### 14.1 Definition of Outcome Measures

The treatment arms will be compared in terms of the following outcome measures:

#### **Primary Outcome Measure**

- Objective clinical response (CR, PR) to neoadjuvant treatment

Objective clinical response as measured by callipers is defined as either a partial or complete response. A complete clinical response (CR) is defined as no palpable lesion from which to take calliper measurements. A partial clinical response (PR) is defined as a decrease in the greatest uni-dimensional measurement by callipers of at least 30%.

Patients who achieve a CR or a PR will be defined as achieving an objective clinical response to neoadjuvant treatment.

## Secondary Outcome Measures

- Objective ultrasound-determined response (CR, PR) to neoadjuvant treatment

Objective ultrasound-determined response is defined as either a partial or complete response. A partial response (PR) is defined as at least a 30% decrease in the longest dimension of the lesion in accordance with RECIST criteria. A complete response (CR) is defined as complete disappearance of the radiological (USS) lesion. Patients who achieve a CR or a PR will be defined as achieving an objective ultrasound-determined response to neoadjuvant treatment.

## Type of surgery

This is a binary outcome recorded as either breast conserving surgery or mastectomy.

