# Trial Schema

### 3. BACKGROUND AND INTRODUCTION

#### 3.1 Current surgical treatment for postmenopausal early breast cancer

The management of early stage breast cancer remains sub-optimal. Standard treatment is primary surgery and subsequent selective adjuvant radiotherapy, hormone therapy and chemotherapy. Larger tumours and those close to the nipple are usually treated by mastectomy whilst smaller more peripheral tumours are often suitable for breast conserving surgery. There is good evidence that body image is just as important to postmenopausal women as it is to younger patients. Neoadjuvant chemotherapy, usually offered to younger patients, can achieve overall survival identical to post-operative chemotherapy but with the additional benefit of less radical surgery. Postmenopausal patients are not routinely given the opportunity of neoadjuvant chemotherapy to downstage their tumours and allow less disfiguring surgery because of concerns about the associated toxicity. Furthermore the large majority of these patients have oestrogen receptor-positive tumours and may thus be less likely to respond well to chemotherapy. However, the proven ability of aromatase inhibitors to downstage these tumours pre-operatively, without the toxicity of chemotherapy, is currently infrequently utilised and is the subject of this study.

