The IMPACT trial randomised 330 women and compared 12 weeks of anastrozole with 12 weeks of tamoxifen and the combination of both agents as neoadjuvant therapy. The overall response rate was 37.2 % for anastrozole, 36.1% for the combination and 39.4% for tamoxifen. In larger tumours where pre-treatment mastectomy was thought to be required anastrozole was associated with a higher probability of downstaging to permit breast conservation. HER-2 expression was observed to predict low response to tamoxifen, with maintained response to anastrozole. However the sample size was small and statistically unreliable. As the P024 and IMPACT studies involved different treatment durations and different inclusion criteria it is not possible to make any firm conclusions from cross comparisons, but the clear difference in response rates between tamoxifen and letrozole is encouraging.

Another study, the PROACT trial, randomised 451 women to receive 12 weeks of anastrozole or tamoxifen treatment before surgery in a double-blind trial in which some patients also received chemotherapy. While the presence of chemotherapy has somewhat complicated the interpretation of this study, anastrozole use was associated with a higher rate of breast conserving surgery over tamoxifen.

Exemestane has been less extensively evaluated as a neoadjuvant therapy. Recently reported studies include a multicentre French trial in which 38 ER positive postmenopausal women requiring mastectomy pre-treatment were treated with exemestane 25 mg/day for 16 weeks. The overall response rate was reported as 70.6%, with 45.2% of women able to undergo breast conserving surgery.

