## 6. PATIENT SELECTION

### 6.1 Inclusion criteria

The study population consists of postmenopausal women diagnosed with resectable breast cancer, who meet the following eligibility criteria:

- Biopsy proven, ER positive invasive breast cancer (where ER positive is defined as equivalent to an ER “Quick or Allred score” of 3 or greater)
- Tumour, measured on U/S, as greater than 2 cm in diameter
- Postmenopausal, defined as:
  - Any Age:- bilateral surgical oophorectomy
    - amenorrhea  $\geq$  5 years (any cause)

Age  $\geq$  50 yrs:- natural amenorrhea for  $\geq$  1 year

Age  $<50$  yrs: - if amenorrhea  $< 5$  years or hysterectomy without bilateral surgical oophorectomy, then FSH, LH and oestradiol must be assayed to confirm postmenopausal status

- Adequate haematological, renal and liver function, defined as a platelets of  $>100 \times 10^9/l$ , white blood cell count of  $>3 \times 10^9/l$ , creatinine  $<110$  mmol/l, AST and/or ALT  $< 1.25 \times$  upper limit of normal
- Patients must be fit to complete surgery for their breast cancer
- Written informed consent
- ECOG performance status 0,1 or 2

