## 14.2 Statistical analysis

The main analysis will be carried out when all patients have completed their neoadjuvant therapy and have had their assessment of response. The main analyses comparing the objective clinical response rates will be carried out with and without adjustment for the additional randomisation; e.g. in the 500 patients receiving celecoxib vs 500 patients receiving celecoxib-placebo, objective clinical response rates will be assessed using the chi-squared test, and repeated using the Mantel-Haenszel test to allow for the adjustment of exemestane or letrozole. An additional pre-planned analysis will be the comparison of the 250 patients in each of the 4 treatment groups using one test statistic; this will be powered to detect larger differences (~13%). We do not plan to carry out multiple comparisons between the 4 treatment groups, instead we will perform one test statistic to determine if there are differences between any of the 4 treatment groups.

The secondary outcomes of survival and local control will be assessed using Kaplan-Meier survival curves, and treatments will be compared using the Log-rank test. The effect of

prognostic factors in addition to treatment will also be assessed using Cox-regression models. All analyses will be carried out on an intention-to-treat basis.

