### **14.3 Sample size**

The trial will accrue a total of 1000 patients.

The objective clinical response rate for patients receiving letrozole is reported to be around 55%, thus randomising 250 patients into each of the 4 treatment arms will allow the detection of an absolute difference of 13% between any of the treatments, with 5% significance and 85% power (Machin and Campbell 1987). Within the 2x2 factorial design, the comparison of the 500 patients receiving celecoxib vs 500 patients receiving placebo will allow the detection of an absolute difference of at least 9% with an 80% power; similarly for 500 patients receiving exemestane vs the 500 patients receiving letrozole. Recruiting 1000 patients will also allow the comparison of the secondary endpoints of type of surgery and biological profiling as well as correlating objective clinical response with overall survival and local control.

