### NEO-EXCEL

Dear Dr  
Regarding your patient \_\_\_\_\_

As she has been diagnosed with an ER positive breast cancer which is >2 cms she has been invited to take part in NEO-EXCEL, a randomised Phase III neoadjuvant trial of pre-operative exemestane or letrozole +/- celecoxib for the treatment of ER positive postmenopausal early breast cancer. This is a multicentre national clinical trial run through the Cancer Research UK Clinical Trials Unit at the University of Birmingham.

The aim of the trial is to see if the addition of a COX 2 inhibitor to an aromatase inhibitor in the neoadjuvant setting produces a greater objective clinical response than an aromatase inhibitor alone. By comparing two aromatase inhibitors we are also investigating whether exemestane is more effective than letrozole neoadjuvantly with and without celecoxib. Celecoxib as a possible treatment for cancer has resulted from an incidental finding that people taking nonsteroidal anti-inflammatory drugs (NSAIDS) for long periods seem to get less of certain cancers such as bowel and breast cancer.

If the neoadjuvant therapy causes the tumour to shrink then less extensive surgery may be possible. Some tumours previously only suitable for mastectomy may become suitable for breast conserving surgery.

We propose to establish a tissue and serum bank for future gene expression profiling and proteomic analysis to answer 2 key questions. Firstly, will expression profiling of sequential tumour biopsies identify molecular mechanisms which underpin the effects of celecoxib in the context of neoadjuvant breast cancer treatment? Secondly we hypothesise that markers of differential response to aromatase inhibitors will be identified in a linked analysis.

The randomisation is:

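### Type of surgery is compared as the final operation in all patients, and the protocol lists no record of the operation planned before treatment, which weakens this secondary outcome as a measure of conversion from mastectomy

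*Protocol*

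**What the plan says.** Section 14.1 defines type of surgery in one sentence: "This is a binary outcome recorded as either breast conserving surgery or mastectomy". It does not refer to what would have been done before treatment.

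The comparison covers everyone randomised. Section 14.2 states: "All analyses will be carried out on an intention-to-treat basis". Section 14.3 relies on the full sample for this endpoint: "Recruiting 1000 patients will also allow the comparison of the secondary endpoints of type of surgery and biological profiling". No power is stated for it.

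The size criterion in section 6.1 is "Tumour, measured on U/S, as greater than 2 cm in diameter"; need for mastectomy is not a condition of entry. Section 3.1 notes that "smaller more peripheral tumours are often suitable for breast conserving surgery", and also names closeness to the nipple as a reason for mastectomy.

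The background treats downstaging as important. Section 3.1 says that the ability of aromatase inhibitors to downstage tumours before surgery "is currently infrequently utilised and is the subject of this study". The GP letter (Appendix 11) says: "Some tumours previously only suitable for mastectomy may become suitable for breast conserving surgery". Section 3.2.1 reports of the anastrozole trial: "In larger tumours where pre-treatment mastectomy was thought to be required anastrozole was associated with a higher probability of downstaging to permit breast conservation". It also cites a French exemestane study of 38 women who all required mastectomy before treatment, of whom 45.2% could have conservation.

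The minimisation factors in section 7 are tumour size (>2-5 cm, >5 cm), grade, ER score, Her2 and low-dose aspirin use. The screening and baseline lists in section 9, and Figure 1, include caliper and ultrasound tumour measurement but no planned operation. Section 10.2 names the CRFs without giving their contents.

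**The concern.** The final operation mixes two groups. In women who would have needed mastectomy, it shows whether treatment made conservation possible. In women already suited to conservation, most will have conservation in either arm, so they can add little or no treatment contrast.

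If the second group is sizeable, a real difference in conversion shrinks in the all-patient comparison. A null result could then mean no conversion benefit, or a benefit diluted by women who had no need to convert. The trial also could not report a conversion rate comparable with the results cited in section 3.2.1 for women judged to need mastectomy.

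This is more than an analysis detail that a SAP could settle. A SAP can define a subset or a stratified test, but it cannot supply a pre-treatment judgement that was never collected. A surgeon asked afterwards would know how the tumour had responded and which aromatase inhibitor had been given open label.

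**Working it through.** **The protocol's own figures.** Section 14.3 gives power for the primary endpoint only. The formula is two-sided 5%, pooled variance, n per group:

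power = Φ{ [ |p2 − p1|·√n − 1.96·√(2p̄(1 − p̄)) ] / √(p1(1 − p1) + p2(1 − p2)) }

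- 55% v 68%, 250 per arm: 85.0% (stated 85%).
- 55% v 64%, 500 per group: 82.7% (stated 80%).

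Both are reproduced, but neither concerns type of surgery.

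**Inputs for the illustration**

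- 500 v 500, from the factorial comparison in section 14.3.
- Conversion of 35% v 45% among women needing mastectomy. These are the conservation rates in section 3.2.1 for tamoxifen v letrozole. Applying them to mastectomy candidates, and to this trial's contrasts, is an assumption.
- Conservation of 95% in both groups among women already suitable, so no treatment effect there. Assumption.
- Share already suitable, s = 30, 50 or 70%. The protocol gives no figure. Assumption.

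**Dilution.** The all-patient conservation rate is (1 − s)·r + s·0.95, where r is the conversion rate. The second term cancels between groups, so the all-patient difference is (1 − s) × 10 points.

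**All-patient comparison at s = 50%.** The rates are 0.5 × 0.35 + 0.5 × 0.95 = 65% and 0.5 × 0.45 + 0.5 × 0.95 = 70%, with p̄ = 0.675.

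- Numerator: 0.05 × √500 − 1.96 × √(2 × 0.675 × 0.325) = 1.118 − 1.298 = −0.180.
- Denominator: √(0.2275 + 0.2100) = 0.661.
- Power = Φ(−0.27) = 39%.

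**Mantel-Haenszel stratified by planned operation at s = 50%.** Each stratum has 250 per group and weight 0.5.

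- Weighted difference: 0.5 × 0.10 + 0.5 × 0 = 0.05.
- Null variance: 0.25 × 2 × 0.40 × 0.60/250 + 0.25 × 2 × 0.95 × 0.05/250 = 0.000480 + 0.000095 = 0.000575, so SE = 0.0240. The unstratified SE is 0.0296.
- z = 0.05/0.0240 = 2.09, and power = Φ(2.09 − 1.96) = 55%.

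**Women planned for mastectomy only at s = 50%.** 35% v 45% with 250 per group gives 63%.

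| Already suitable | All-patient rates | Power, all patients | Power, stratified | Power, mastectomy-planned (n per group) |
|---|---|---|---|---|
| 30% | 53% v 60% | 61% | 74% | 77% (350) |
| 50% | 65% v 70% | 39% | 55% | 63% (250) |
| 70% | 77% v 80% | 21% | 31% | 42% (150) |

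If every woman needed mastectomy, power would be 90%. The 95% assumption matters little: with 90% to 100% conservation among women already suitable, all-patient power at s = 50% runs from 38% to 41%.

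**The case against.** Much of the opposing case stands.

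- **Status of the outcome.** A reader of section 3.1 might infer that downstaging is the question the trial formally sets out to answer. The documents do not support that. The stated objective (sections 2 and 5) is superiority of exemestane and enhancement by celecoxib, and the primary outcome is clinical response. Type of surgery is one of seven secondary outcomes. The GP letter also gives clinical response as the aim and conversion only as a possible benefit.
- **Whether a record exists.** A reader might infer that the planned operation is recorded nowhere. That cannot be established, because the contents of the Randomisation and On-study Forms are not shown. The text shows only that the protocol does not list the item.
- **Separating the groups afterwards.** It is tempting to say that the two groups can never be distinguished. Baseline size is measured and is a minimisation factor, so adjustment by size would recover part of the loss. It remains a partial proxy, because the >2-5 cm band is wide and section 3.1 also names closeness to the nipple.
- **Validity.** The all-patient comparison is randomised and unbiased, and the proportion of women ending with mastectomy is a legitimate quantity in itself. It should not be replaced.
- **Size.** The conversion rates come from a letrozole v tamoxifen comparison that the protocol does not describe as limited to mastectomy candidates. The other inputs are assumed. The calculation ignores what adjustment by size could recover, so it may overstate the loss.
- **Remedy.** In these scenarios even the mastectomy-planned comparison stays below 80% power. The item improves sensitivity and interpretation, but does not turn this into a well-powered endpoint.

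The data-collection point remains: the judgement has to be recorded before allocation.

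**Conclusion.** The point holds as a limit on the sensitivity and interpretation of one secondary outcome. It does not show bias, contradiction or a threat to the primary analysis. Entry admits women already suited to conservation, the outcome is the final operation in everyone, and no pre-treatment planned operation is listed among the assessments or minimisation factors.

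If women already suitable show no treatment effect, the all-patient difference is the conversion difference times the share needing mastectomy, whatever that share is. The size of the loss here is not known. Under the stated assumptions, stratifying by planned operation raises power from 61 to 74%, 39 to 55%, or 21 to 31% as the share already suitable goes from 30 to 50 to 70%. These figures illustrate the mechanism and are not forecasts for exemestane v letrozole or celecoxib v placebo.

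**What to change.** Add one mandatory item to the Randomisation or On-study Form, completed before allocation: the operation the surgeon would perform today, mastectomy or breast conserving. If the forms already hold it, state it in sections 7 and 9.

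In sections 14.1 and 14.2, keep the all-patient comparison of type of surgery but stratify it by this item. Pre-specify alongside it the conservation rate among women recorded as needing mastectomy.

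The cost is one tick-box and a short change of wording, with no added visit or procedure. Section 10.2 lets CRFs be changed without a protocol amendment, so collection could start at once; the change to section 14 would follow by amendment. There are two drawbacks. The item is a surgeon's judgement, although before allocation its errors cannot depend on the arm. It will also be missing for patients already randomised, who could be stratified by baseline tumour size or kept as a separate stratum.
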